#### **Treatment of patients unable to tolerate oral medication**

If a patient develops a short term intolerance of oral medication after the initial dose of study medication, study drug may be temporarily interrupted (Section 6.5.5), alternatively, administration of ERL suspension may be carried out via a nasogastric (NG) tube as described below. Such administration of study drug via NG tube will be recorded on the Immunosuppressive Therapy CRF. If this period is more than 21 consecutive days or more than two episodes of 7 days or longer, study drug discontinuation will be discussed among the study team including the study nephrologists. Patients should be returned to oral medication as soon as possible after such an interruption of administration of study medication by mouth.

#### **Nasogastric administration of Everolimus (Patients randomized to everolimus)**

Everolimus may be administered via an NG tube until tablets can be tolerated. In order to guarantee adequate dosing the following handling instructions for the application of everolimus tablets via NG tube should be closely followed:

- Do not use any special crushing equipment.
- Pour the tablets into a small (plastic or glass) medicine beaker which contains 10 ml drinking water and wait about 10 minutes.
- Then crush the tablets gently, using the back of a spoon until only small particles are visible.

- Stir the dispersion gently, pull the dispersion into a syringe and inject into the NG tube.
- Rinse the beaker (and the spoon) 3 times with 5 ml drinking water and inject into the tube.
- Finally flush the tube with 10 ml drinking water.

### **6.5.7 Other concomitant treatments**

#### **6.5.7.1 Background immunosuppressive therapy**

##### **Induction Therapy:**

Campath (Alemtuzumab) 30 mg or Simulect (basiliximab) 20 mg will be administered at induction of anesthesia along with Solumedrol 500 mg intravenously. Basiliximab 20 mg will also be given intravenously on day 4 post-transplant.

#### **6.5.7.2 Initiation and maintenance of Tacrolimus**

It is recommended that the initial dose of TAC be administered according to our standard of care practice within 24 hours after reperfusion of the graft. If patients experience DGF, TAC can be held for up to and including 14 days. However, TAC or study medication (ERL or MMF/MPA) must be started within 24 hours post-transplant. Subsequently, ERL dosing will be adjusted according to trough level results from the reference laboratory. Tacrolimus whole-blood trough concentrations will be determined on all study visits. Target TAC trough levels will be as follows in Table 6-1. Target therapeutic ranges for TAC C0-h levels in whole blood will be assessed at the hospital laboratory for purposes of this protocol.

If, for any time throughout the study, TAC is held for > 14 days, ERL should be discontinued and the patient discontinued from the study. These patients should be followed throughout the remainder of the study to Month 24 on a follow-up schedule. See Section 7.5, Safety assessments, Follow-up of prematurely discontinued patients.

**Table 6-1 Target therapeutic ranges for Tacrolimus C0-h levels in whole blood**

Randomization Arm	Time Post-transplant and Corresponding Levels		
	0 – 3 months	3 – 12 months	12 – 24 months
Arm 1 (Everolimus)	4 - 7 ng/mL	2 – 5 ng/mL	2 - 5 ng/mL
Arm 2 (Everolimus)	4 - 7 ng/mL	0 ng/mL	0 ng/mL
Arm 3 (MMF/MPA)	8 - 12 ng/mL	8 - 12 ng/mL	6 - 8 ng/mL

#### **6.5.7.3 Initiation and maintenance of steroids**

Intravenous and oral steroids will be administered and withdrawn according to the standard of practice at our institution. For the cases that require maintenance steroid therapy, 5-10 mg/day is allowed per our institutional practice.

Dosing and changes of steroid dosing will be recorded in the Immunosuppressive Therapies CRF.

#### **6.5.7.4 Cytomegalovirus prophylaxis for viremia or viruria**

CMV prophylaxis with Valcyte for a minimum of 90 days is mandatory for all cases at our institution. Treatment with ganciclovir, cytomegalovirus hyperimmune globulin, acyclovir or valacyclovir will be administered according to our standard practice. All cases of CMV positive donors to CMV negative recipients will be treated with Valcyte for 6 months according to our standard practice. CMV prophylaxis may also be given following any antibody treatment of acute rejection episodes.

#### **6.5.7.5 BK viremia or viruria**

Patients with BK viremia or viruria should be treated according to our institutional practice. Patients whose BKV treatment includes a reduction of immunosuppression can remain in the study if the ERL trough level remains between 3 ng/mL and 8 ng/mL or the MMF/MPA dose remains stable. Patients treated with antiviral therapy can remain in the study.

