### **3.2 Secondary objectives**

The key secondary objective is to compare renal function of the everolimus treatment arms to the MMF/MPA treatment arm at 12 and 24 months post-transplantation. Renal function will be measured by the calculated glomerular filtration rate (GFR), using the MDRD (Modification of Diet in Renal Disease) formula (20).

Other secondary objectives include:

- The incidence of treated BPAR at 12 months
- The incidence of graft loss at 12 months
- The incidence of death or loss to follow up at 12 months
- Incidence of adverse events (AEs)
- Incidence of serious adverse events (SAEs)
- Incidence of new onset diabetes mellitus defined as non-diabetic patients before transplantation, who are receiving glucose lowering treatment for more than 30 days

post-transplant, or with a random plasma glucose  $\geq 200$  mg/dL (11.1 mmol/L) with 2 fasting plasma glucose values  $\geq 126$  mg/dL (7 mmol/L).

- Incidence of CMV (viremia or viruria) and BKV (viremia or viruria)
- Incidence of proteinuria by more than 3 fold or proteinuria reaching 1.5gm/day
- The comparison of the health related quality of life for patients treated with everolimus plus low dose tacrolimus to CellCept plus standard dose tacrolimus

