#### **6.5.5 Permitted study drug dose adjustments and interruptions**

For patients who are unable to tolerate the protocol-specified dosing scheme, dose adjustments and interruptions are permitted in order to keep the patient on study drug. The following guidelines should be followed:

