## **Everolimus and MMF/MPA guidelines for dose reductions for safety reasons:**

For patients who are unable to tolerate the protocol-specified dosing schedule, dose adjustments are permitted in order to keep the patient on study drug. Reasons for study drug dose reductions may be for example, a decrease in the white blood cell count or platelet count, an increase in cholesterol or triglyceride level, gastrointestinal intolerance or other adverse events. Severe and unremitting changes may lead to study drug discontinuation. If study medication (ERL or MMF/MPA) is interrupted for safety reasons for 2 episodes of  $\geq 7$  consecutive days, or more than 21 consecutive days, discontinuation of study medication should be discussed with the sponsor.

During the course of the trial the study drugs will be administered on a BID regimen. Study medication will not be provided to patients after they have discontinued the study.

- Everolimus 1.5 mg treatment groups
  - It is recommended to reduce the dosing from the standard 0.75 mg BID to 0.5 mg BID. The dosing should, however, always follow a BID schedule.
- MMF/MPA 2,000/1,440 mg treatment group
  - MMF/MPA dose can be adjusted for gastrointestinal intolerance or a decrease in WBC. If neutropenia develops ( $ANC < 1,300/\text{mm}^3$ ) dosing with MMF/MPA should be interrupted or reduced, appropriate diagnostic tests performed and the patient managed according to local practice.

Additional information for dose adjustments based on laboratory values or other adverse events may be found in Appendix 3.

All changes in dosing of the investigational and control drug must be recorded on the Study Drug Dosage Administration Record CRF with date and reason.

The TAC dose must be adjusted to get  $C_{0-h}$  value within the pre-specified target range: for ERL Arm 1: 4 - 7 ng/mL from Day 1 until Month 3, and 2 - 5 ng/mL starting at the Month 3 Visit; for ERL Arm 2: 4 – 7 ng/mL from Day 1 until Month 3, where the patient will be converted from TAC to MMF/MPA; for SOC arm 3: 8 - 12 ng/mL starting at Day 1 until

Month 12, and 6 – 8 ng/mL from Month 12 until study completion. If TAC is held for > 14 days, study drug should be discontinued and the patient discontinued from the study.

These changes must be recorded on the Dosage Administration Record CRF.

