Patients who discontinue study drug prior to the 24 month treatment period will be contacted at scheduled months 6, 12, 18 and 24 visits to obtain follow-up information and should not be considered withdrawn from the study. Information will be collected on vital signs, hospitalizations, rejection episodes, lab results (proteinuria and serum creatinine),

graft loss/re-transplant, SAEs, malignancies, opportunistic infections, patient survival, CMV infections and immunosuppressive therapy. In addition, major adverse cardiac events (MACE) will be reported during the follow-up period as a Serious Adverse Event (SAE). These include acute myocardial infarction, congestive heart failure, percutaneous coronary intervention (PCI), automatic implanted cardiac defibrillator (AICD), coronary artery bypass graft surgery (CABG), cerebral vascular accident, and peripheral vascular disease.

Biopsies will be obtained at 3, 12 and 24 months post-transplantation for all patients who agree to have this procedure done. Biopsies will be obtained at 3 months and 1-year post-transplantation biopsies are performed as a part of standard institutional protocol.

If patients refuse to return for these visits or are unable to do so, every effort should be made to contact them or a knowledgeable informant by telephone to determine the information on survival status, graft loss/re-transplant, rejection episodes, malignancies, opportunistic infections and immunosuppressive therapies. Since patients will be followed even after discontinuation of study medication, the Study Completion CRF page should only be completed at Month 24 or earlier if the patient can no longer be followed, e.g. death, lost to follow-up, withdrawal of consent.

No study drug will be provided for patients who discontinue study medication prior to study completion at 24 months.

See Section 7 for the required assessments of these patients after study drug discontinuation.

For patients who are lost to follow-up (i.e. those patients whose status is unclear because they fail to appear for study visits without stating an intention to withdraw), the investigator /the study team will show "due diligence" by documenting in the source documents steps taken to contact the patient, e.g. dates of telephone calls, registered letters, etc.

Patients who are prematurely withdrawn from the study will not be replaced by an equal number of newly enrolled patients.

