#### **10.4.1 Variable**

The primary efficacy variable is the composite efficacy failure rate (treated BPAR, graft loss, death or loss to follow-up) at 6, 12 and 24 months post-transplant. The secondary variable is renal function assessed as eGFR during the first 24 months post-transplantation, determined by the MDRD formula. Other secondary variables include the incidences of CMV and BKV, new onset diabetes mellitus, chronic kidney disease with associated proteinuria, adverse events, serious adverse events and tacrolimus associated adverse events.

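### The BK virus rule in 6.5.7.5 makes staying in the study depend on a secondary outcome and on a test that differs by arm, and it does not fit 6.5.5 or 6.5.8

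*Combined protocol and SAP*

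**What the plan says.** Section 6.5.7.5 leaves BK virus treatment to institutional practice. Where that treatment includes less immunosuppression, patients "can remain in the study if the ERL trough level remains between 3 ng/mL and 8 ng/mL or the MMF/MPA dose remains stable". It then adds, with no condition: "Patients treated with antiviral therapy can remain in the study". It does not say what happens to a patient who meets neither limb, does not define a stable dose, and does not mention tacrolimus.

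BK virus is also a trial outcome. Section 3.2 lists its incidence as a secondary objective, and section 10.4.1 says: "Other secondary variables include the incidences of CMV and BKV".

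Section 6.5.5 sets a different tone for dose changes. It opens by saying that "dose adjustments and interruptions are permitted in order to keep the patient on study drug", and its part on safety reductions repeats that "dose adjustments are permitted in order to keep the patient on study drug". The reasons given there are an open list of examples that includes other adverse events. An everolimus trough outside range is met with a dose change, and from Month 3 the target narrows to 5-8 ng/mL.

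Section 6.5.8 lists the circumstances that require study drug to stop. The list has an everolimus trough at or below 3 ng/mL that cannot be maintained. It has no BK virus item, no MMF/MPA dose item and no upper trough limit. Patients who stop drug early are contacted at Months 6, 12, 18 and 24 "to obtain follow-up information and should not be considered withdrawn from the study".

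**The concern.** The condition in 6.5.7.5 governs being in the study, not only being on study drug. If failing it means leaving, retention depends on an event after randomization that is itself compared between arms, and on a test that is not the same in each arm. The trial is open label, so those applying the test know the arm.

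Three things could be affected. If contact with the patient ends, 10.4.3 makes that patient a loss to follow-up, which the primary composite in 10.4.1 counts as failure. If contact ends but the patient is not scored that way, later rejections, graft losses and eGFR values are missing. And if contact continues on the reduced schedule, the patient can still be treated as not having completed, and so drop out of the per-protocol set defined in 10.1.

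**Working it through.** No figure in the plan depends on this rule, so there is nothing to reproduce. The check is a comparison of sections, followed by arithmetic for scale.

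**1. The test by arm under 6.5.7.5**

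| Arm | What is tested | Consequence |
|---|---|---|
| 1 | Everolimus trough within 3-8 ng/mL | The everolimus dose may fall as long as the trough stays in the band |
| 2, after Month 3 | On everolimus and MMF/MPA | Not stated whether one limb is enough |
| 3 | MMF/MPA dose stable | The dose itself is tested, with no definition of stable |

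**2. Against 6.5.5.** An MMF/MPA reduction for gastrointestinal intolerance or low white cells carries no consequence for study participation. The same reduction made for BK virus fails the MMF/MPA limb of 6.5.7.5. A trough above 8 ng/mL leads to a dose change in 6.5.5 but breaks the everolimus limb of 6.5.7.5. From Month 3 the two sections also use different bands: 5-8 against 3-8 ng/mL.

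**3. Against 6.5.8.** The lower trough limit largely agrees with the 6.5.8 trigger, apart from a trough of exactly 3 ng/mL. The conflict lies in the MMF/MPA limb, in the upper trough limit, and in leaving the study as opposed to stopping drug.

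**4. Does leaving end follow-up?** Section 4 puts all withdrawn patients on a reduced schedule. The synopsis follows discontinued patients at Months 3, 6, 12 and 24. Section 6.5.8 uses Months 6, 12, 18 and 24, and the follow-up text after 7.5.11 uses Months 6, 12 and 24. Section 6.5.7.2, for patients taken off the study after a tacrolimus hold, says expressly that they are followed to Month 24. Section 6.5.7.5 has no such sentence.

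**5. Visits lost on the reduced schedule.** For a patient who leaves just after Month 3, Table 7-1 has nine visits left (Months 4, 6, 8, 10, 12, 15, 18, 21, 24). The 6.5.8 schedule has four (Months 6, 12, 18, 24). The difference is 9 - 4 = 5.

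**6. Scale if contact does end.** With n = 16 per arm (10.6), k patients scored as lost who would not otherwise have failed add k/16 to that arm's failure rate:
- k = 1: 1/16 = 6.25 points
- k = 2: 2/16 = 12.5 points
- k = 3: 3/16 = 18.75 points

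The documents give no BK virus rate. Let p be an assumed proportion of an arm that fails the condition. Expected number = 16p, and the chance of at least one = 1 - (1 - p)^16:
- p = 5%: 0.8 patients; 1 - 0.95^16 = 56%
- p = 10%: 1.6 patients; 1 - 0.90^16 = 81%
- p = 20%: 3.2 patients; 1 - 0.80^16 = 97%

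These values of p are illustrations only.

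**The case against.** The strongest reply is that the protocol already follows these patients. The places in step 4 provide contact after discontinuation or withdrawal, and the only stated exceptions are death, loss to follow-up and withdrawn consent. Section 6.5.8 describes loss to follow-up as unclear status after missed visits, which does not fit a patient who is still being contacted. The FAS keeps every randomized patient who took a dose. This reply stands: as written, the plan does not make BK virus patients primary failures.

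Two further points also stand. Section 6.5.7.5 says patients can remain if the condition holds; it does not say that others must leave, and 6.5.8 lists no such reason. A reader might take from it a firm rule that any MMF/MPA change for BK virus removes the patient. That is an inference, although the sentence has little function without it. A reader might also conclude that the test is harshest in the control arm. The documents do not show this. The rule places no limit on lowering tacrolimus, and Arm 3 has the highest tacrolimus targets (Table 6-1), so an Arm 3 patient whose tacrolimus is cut while MMF/MPA is stable meets the condition.

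The reply does not remove the contradiction. Section 6.5.8 is itself mixed, since its opening also speaks of withdrawal from the trial, and one of its follow-up paragraphs names only patients who stop everolimus. Section 7.5.11 uses being dropped from the study with no follow-up stated. A site could reasonably read 6.5.7.5 as ending participation.

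**Conclusion.** The contradiction is real and needs no rate to establish. Section 6.5.7.5 ties study participation to BK virus management through tests that differ by arm and are undefined for Arm 2 on both drugs, while 6.5.5 and 6.5.8 point the other way. Followed by its natural implication, it moves patients to a reduced schedule, and can take them out of the per-protocol set, by outcome and by arm.

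The effect on the FAS primary comparison is conditional. It arises only if a site ends contact before Month 24, and it is then 6.25 points of an arm for each patient scored as lost who would not otherwise have failed. A reader might go further: assume that 10-20% of Arm 3 have such a dose reduction and infer 10-20 points of excess failure. The documents do not support that. The rate is not in them, and the result also requires that every such patient is scored as lost, that none would have failed anyway, and that no one is removed in the comparator arms.

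**What to change.** Amend 6.5.7.5 so that it agrees with 6.5.5 and 6.5.8:

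- State that BK virus management, or study drug discontinuation that results from it, does not end study follow-up in any arm.
- State that these patients are followed to Month 24 on the existing schedule and are not counted as lost to follow-up while contact continues.
- Have the sponsor settle, for each arm and for Arm 2 after Month 3 in particular, whether any condition applies to staying on study drug, and word it consistently with 6.5.5 and the 6.5.8 list, with stable defined if the term is kept. No dose or trough rule is proposed here.
- State in 10.1 whether a patient who stops study drug because of BK virus but is followed to Month 24 counts as having completed the study.

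The cost is about one paragraph of amendment text, since the visits already exist in 6.5.8 and Table 7-1. The small downside is that some retained patients will be on modified regimens, which the intent-to-treat analysis already accepts.

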#### **6.5.7.6 *Pneumocystis carinii* pneumonia prophylaxis**

All patients will be started on trimethoprim-sulfamethoxazole, starting when oral medication can be tolerated and continuing for the 3 to 6 months post-transplant, in accordance with MGTI standard practice. Aerosolized pentamidine or dapsone may be administered to patients unable to tolerate trimethoprim-sulfamethoxazole.

#### **6.5.7.7 Treatment of oral Candida**

For oral thrush (Candida) Nystatin may be used in a swish and swallow regimen, alternatively clotrimazole (Mycelex) lozenges/troches may be used. Routine use of systemic agents (i.e. itraconazole, voriconazole and fluconazole) will not be allowed unless patients are systemically infected. Administration of azoles may increase blood concentrations of everolimus; therefore their use should be minimized. Particular attention to side effects is required (see Appendix 4).

#### **6.5.7.8 Lipid lowering medications**

HMG CoA reductase inhibitors (e.g., fluvastatin) are to be administered according to our standard practice for the management of hyperlipidemia. Patients requiring treatment with this class of medication (especially lovastatin) should be monitored closely for signs of rhabdomyolysis, such as, dark-colored urine, fever, muscle cramps, pain, spasm, or stiffness, unusual tiredness or weakness. Lipid lowering therapy should be optimized before dosage reduction of study medication is considered (see Appendix 4).

#### **6.5.7.9 Other medications**

The investigator and the study team will instruct the patient to notify the study site about any new medications he/she takes after the start of the study drug. All medications (other than study drug) and significant non-drug therapies (including physical therapy and blood transfusions) administered after the patient starts treatment with study drug must be listed on the Concomitant Medications/Significant Non-Drug Therapies after Start of Study Drug CRF. If administered for an adverse event (AE), it should be appropriately cross-referenced on the AE CRF.

All other immunosuppressive drugs other than those specified in the protocol are disallowed except those needed to treat rejection.

### **6.5.8 Study drug discontinuation and premature patient withdrawal**

Study drug must be discontinued and the patient withdrawn from the trial if the investigator determines that continuing it would result in a significant safety risk for that patient. The following circumstances require study drug discontinuation:

- Withdrawal of informed consent
- Pregnancy
- Use of immunosuppressive drugs other than those specified by protocol except those needed to treat acute rejection.
- If the everolimus trough level is  $\leq 3\text{ng/mL}$  and cannot be maintained.
- If tacrolimus is held for more than 14 days.
- Any other protocol deviation that results in a significant risk to the patient's safety

If study drug (ERL or MMF/MPA) is interrupted for longer than 21 consecutive days or more than 2 episodes of 7 days or longer, discontinuation of study drug should be considered and discussed with the sponsor.

For patients prematurely discontinuing ERL, a post-study follow-up contact will be made at Month 3, 6, 12, 18 and 24 after transplantation, except in patients who prematurely discontinue ERL due to death, lost to follow up or patient withdrew consent. Information will be collected on serum creatinine levels, urea, rejection episodes, graft loss/ re-transplant, malignancies, opportunistic infections, patient survival and current immunosuppressive therapy.

Patients who prematurely discontinued ERL will be followed for any serious adverse event (SAE) occurring within 30 days following the last dose of ERL. These SAEs should be reported to appropriate regulatory authorities.

In addition to these requirements for study drug discontinuation, the investigator should discontinue study drug for a given patient if, on balance, he thinks that continuation would be detrimental to the patient's well-being.

A Study Drug Discontinuation form should be completed, giving the date and primary reason for stopping the study drug.

Patients may voluntarily withdraw from the study for any reason at any time. They may be considered withdrawn if they state an intention to withdraw, or fail to return for visits, or become lost to follow up for any other reason. If premature withdrawal occurs for any reason, the investigator must determine the primary reason for a patient's premature withdrawal from the study and record this information on the Study Completion CRF.

Patients who discontinue study drug prior to the 24 month treatment period will be contacted at scheduled months 6, 12, 18 and 24 visits to obtain follow-up information and should not be considered withdrawn from the study. Information will be collected on vital signs, hospitalizations, rejection episodes, lab results (proteinuria and serum creatinine),

graft loss/re-transplant, SAEs, malignancies, opportunistic infections, patient survival, CMV infections and immunosuppressive therapy. In addition, major adverse cardiac events (MACE) will be reported during the follow-up period as a Serious Adverse Event (SAE). These include acute myocardial infarction, congestive heart failure, percutaneous coronary intervention (PCI), automatic implanted cardiac defibrillator (AICD), coronary artery bypass graft surgery (CABG), cerebral vascular accident, and peripheral vascular disease.

Biopsies will be obtained at 3, 12 and 24 months post-transplantation for all patients who agree to have this procedure done. Biopsies will be obtained at 3 months and 1-year post-transplantation biopsies are performed as a part of standard institutional protocol.

If patients refuse to return for these visits or are unable to do so, every effort should be made to contact them or a knowledgeable informant by telephone to determine the information on survival status, graft loss/re-transplant, rejection episodes, malignancies, opportunistic infections and immunosuppressive therapies. Since patients will be followed even after discontinuation of study medication, the Study Completion CRF page should only be completed at Month 24 or earlier if the patient can no longer be followed, e.g. death, lost to follow-up, withdrawal of consent.

No study drug will be provided for patients who discontinue study medication prior to study completion at 24 months.

See Section 7 for the required assessments of these patients after study drug discontinuation.

For patients who are lost to follow-up (i.e. those patients whose status is unclear because they fail to appear for study visits without stating an intention to withdraw), the investigator /the study team will show "due diligence" by documenting in the source documents steps taken to contact the patient, e.g. dates of telephone calls, registered letters, etc.

Patients who are prematurely withdrawn from the study will not be replaced by an equal number of newly enrolled patients.

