**Recruitment/Treatment Periods:**

The recruitment period is planned for 24 months. The treatment period is 24 months. A biopsy will be required at Month 3, 12 and 24. Month 3 and 12 biopsies are done according to the institutional practice. No follow-up period is planned. Discontinued patients will be followed for renal function and incidence of efficacy failure at 3, 6, 12, and 24 months post-randomization. Serious adverse events will be recorded for 4 weeks after completing treatment.

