### **Premature study discontinuation and follow-up**

For all patients prematurely discontinuing study medication, a post-study follow-up contact will be made at 6, 12, and 24 months after transplantation, except in patients who prematurely discontinue study medication due to death, lost to follow up or patient withdrew consent. Information on allograft and patient survival, malignancies, rejection episodes, and current immunosuppressive regimen will be collected. A blood sample will also be collected for serum creatinine. All patients will be contacted 30 days after the last dose of study medication regarding Serious Adverse Event information. Graft loss, death and malignancy are Serious Adverse Events and should be entered on a SAE form and

reported to the relevant authorities during the follow-up period (beyond 30 days after the last dose). Other Serious Adverse Events that are related to study medication as assessed by the investigator should also be entered on a SAE form and reported to the IRB and other relevant authorities during the follow-up period.

Clinically notable laboratory abnormalities present at the time of discontinuation will be followed until the abnormality is no longer considered clinically significant.

This will be captured on the Study Completion CRF. Reason must be provided.

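### Follow-up after stopping study drug is stated on four schedules with different contents, so diabetes, virus and proteinuria incidences may be ascertained less fully off drug

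*Combined protocol and SAP*

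**What the plan says.** Four places set a contact list for patients who stop study drug early.

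- Synopsis, Recruitment/Treatment Periods: "Discontinued patients will be followed for renal function and incidence of efficacy failure at 3, 6, 12, and 24 months post-randomization".
- Section 6.5.8, in a paragraph limited to everolimus: "For patients prematurely discontinuing ERL, a post-study follow-up contact will be made at Month 3, 6, 12, 18 and 24 after transplantation". Its content: "Information will be collected on serum creatinine levels, urea, rejection episodes, graft loss/ re-transplant, malignancies, opportunistic infections, patient survival and current immunosuppressive therapy".
- Section 6.5.8, in a later paragraph covering any study drug: "Patients who discontinue study drug prior to the 24 month treatment period will be contacted at scheduled months 6, 12, 18 and 24 visits". These patients are not to be treated as withdrawn. The content runs "Information will be collected on vital signs, hospitalizations, rejection episodes, lab results (proteinuria and serum creatinine" and, once that bracket closes, "graft loss/re-transplant, SAEs, malignancies, opportunistic infections, patient survival, CMV infections and immunosuppressive therapy".
- Premature study discontinuation and follow-up (within Section 7.5), for any study medication: "a post-study follow-up contact will be made at 6, 12, and 24 months after transplantation". Its content: "Information on allograft and patient survival, malignancies, rejection episodes, and current immunosuppressive regimen will be collected", plus a serum creatinine sample.

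Two further places repeat one of these month sets. The Follow-up record row of Table 7-1 uses 3, 6, 12, 18 and 24 months, counted from first dose. The telephone fallback in Section 7 uses 6, 12 and 24. Section 7 also tells off-drug patients to come back for what Table 7-1 indicates, with a creatinine sample, while Section 4 puts withdrawn patients on a reduced schedule.

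On the analysis side, Section 10.1 keeps in the Safety Set anyone who was dosed and then had a safety assessment. Section 10.5.2 compares the incidences of new onset diabetes, CMV, BKV and proteinuria on that set with a Cochran-Mantel-Haenszel test.

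**The concern.** Staff following an off-drug patient will collect different data depending on which page they open. For rejection, graft loss and survival this hardly matters. It does matter for the outcomes that Section 3.2 defines by laboratory results or treatment: diabetes by plasma glucose or by more than 30 days of glucose-lowering treatment, CMV and BKV by viremia or viruria, and proteinuria by a more than threefold rise or 1.5 g/day.

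If such an event is looked for less often after stopping, and the analysis sets no at-risk period, the patient stays in the denominator and is counted as event-free by default. Should the arms also stop at different rates, these named secondary outcomes would be compared on unequal ascertainment.

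**Working it through.** **Step 1: the lists side by side.** OI means covered at most by the general item on opportunistic infections.

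| Source | Months | Clock | Applies to | Proteinuria | CMV | BKV | Glucose or diabetes treatment |
|---|---|---|---|---|---|---|---|
| Synopsis | 3, 6, 12, 24 | randomization | any discontinued patient | not named | no | no | no |
| 6.5.8, everolimus paragraph | 3, 6, 12, 18, 24 | transplantation | everolimus only | no | OI | OI | no |
| 6.5.8, any-drug paragraph | 6, 12, 18, 24 | scheduled visits | any study drug | yes | yes | OI | no |
| Section 7, telephone fallback | 6, 12, 24 | not stated | those who do not return | no | OI | OI | no |
| Table 7-1, Follow-up record | 3, 6, 12, 18, 24 | first dose | any study medication | content not given | content not given | content not given | content not given |
| 7.5, follow-up text | 6, 12, 24 | transplantation | any study medication | no | no | no | no |

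This gives four distinct month sets and three named clocks. Under Section 4, randomization and first dose fall within 24 hours of transplantation, so the clocks differ by about a day; the months and contents matter more. The synopsis says only renal function, which Section 7.4.6 could be read to extend to the urine protein/creatinine ratio.

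**Step 2: scheduled measurements on and off drug.** Sections 7.5.8 and 7.5.9 give chemistry and urine protein at Months 2, 3, 4, 6, 8, 10, 12, 15, 18, 21 and 24, which is 11. Section 7.5.11 gives 5 post-transplant viral tests (Months 3, 6, 12, 18, 24).

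- Stop at Month 1: 11 chemistry/urine and 5 viral tests on the full schedule, against 4 contacts (synopsis), 5 (everolimus paragraph), 4 (any-drug paragraph) or 3 (7.5 text). Proteinuria is collected 4 times under the any-drug paragraph; the everolimus paragraph and the 7.5 text do not name it. No list names a glucose or viral test. CMV infections are collected as information at the 4 any-drug contacts.
- Stop at Month 6: 7 chemistry/urine and 3 viral tests, against 2 or 3 contacts.

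**Step 3: does the analysis compensate?** The explicit imputation rule in Section 10.4.3 is for eGFR. Kaplan-Meier analysis is planned for efficacy failure and its components (10.4.4, 10.5.1). Section 10.5.2 gives no at-risk period or censoring rule for the safety incidences.

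**Step 4: illustrative size.** The plan gives no figure to reproduce. Let p be the true incidence (the same in both arms), f the fraction stopping, h the share of a stopper's events that arise after stopping, and d the chance that such an event is still detected. Then

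observed incidence = p × (1 − f × h × (1 − d)).

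All values of p, f, h and d are assumptions. With p = 25%, h = 0.5, d = 0:

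- f = 30% against 10%: 25% × 0.85 = 21.25% against 25% × 0.95 = 23.75%. The difference is 2.5 points, and 16 × 0.025 = 0.4 patient.
- f = 50% against 10%: 25% × 0.75 = 18.75% against 23.75%. The difference is 5 points, and 16 × 0.05 = 0.8 patient.
- f = 20% in both arms: 25% × 0.90 = 22.5% in each. The difference is 0.

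Setting d = 0.5 halves every difference. With p from 10% to 50% and d from 0 to 0.5, stopping of 30% against 10% gives 0.5 to 5 points. Stopping of 40% against 10% gives 0.75 to 7.5 points, or 0.12 to 1.2 patients of 16.

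**The case against.** The best reply is that off-drug patients may be on the full schedule. Section 6.5.8 sends the reader to Section 7, which says they return for what Table 7-1 indicates, including a creatinine sample. The Follow-up record row mentions no blood sample, so the sentence can be read as pointing to the laboratory and viral serology rows. On that reading the gap closes. Against it, Section 4 says the schedule is reduced, that row is the only one in Table 7-1 written for these patients, and the separate lists would then serve no purpose. The documents leave the matter unclear, and that is part of the point.

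Other routes of capture exist. Section 7 requires final-visit assessments at stopping, which cover virus, glucose and urine protein up to that date. Adverse events are still asked about at visits, infections are logged as needed, Section 6.5.7.9 states no end to medication recording at drug stop, and Section 7.4.3 calls for biopsy when viral infection is suspected. These help, but none schedules a viral or glucose test after stopping.

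A reader might infer three stronger things that the documents do not support.

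- That nobody looks for these events off drug: the any-drug paragraph of 6.5.8 collects proteinuria and CMV, and the full-schedule reading remains open.
- That everolimus patients are followed less well: their months match the all-arm row of Table 7-1, and the any-drug texts cover them too.
- That the arm with more stopping will look safer by a known amount: this needs unequal stopping. Section 6.5.8 has an everolimus-specific trough criterion. Section 4 withdraws patients after everolimus has been held for more than 14 days, while Sections 6.5.5 and 6.5.8 call for discussion after more than 21 days for either drug. Those passages must be reconciled. They make unequal stopping plausible but give no rates, and the 20% dropout in Section 10.6 is not split by arm.

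**Conclusion.** The inconsistency is established from the text alone and should be resolved. There are four month sets, three clocks and differing contents; proteinuria and CMV are named in only one list, and BKV, glucose and diabetes treatment in none. It is also unclear which rows of Table 7-1 apply off drug. Because Section 10.5.2 compares these outcomes as incidences without an at-risk period, off-drug patients may be counted event-free with less ascertainment than on-drug patients.

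Bias between arms is conditional on different stopping rates, so any magnitude is illustrative. At an assumed 25% incidence it stays under one patient per arm of 16 even with no off-drug detection and 50% against 10% stopping; with equal stopping it is zero.

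The composite endpoint is little affected. Every list includes Months 6, 12 and 24, the primary assessment times, and the detailed lists all collect rejection, graft loss and survival. Creatinine at Months 12 and 24, the key renal time points in Section 3.2, is in each detailed list. Whether it exists at Months 3 and 18 depends on the page followed, but no eGFR comparison specific to those months is planned.

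**What to change.** Reconcile the synopsis, Section 4, both paragraphs of 6.5.8, Section 7, Table 7-1 and the follow-up text in Section 7.5 into one off-drug schedule, with one clock, for all arms and any study drug. Table 7-1's 3, 6, 12, 18 and 24 months would serve as an example. State in Section 7 which Table 7-1 rows apply after stopping.

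Keep everything the any-drug paragraph of 6.5.8 already collects: vital signs, hospitalizations, rejection, graft loss, SAEs including major cardiac events, malignancies, opportunistic infections, survival, CMV, immunosuppression, creatinine and proteinuria. Add BKV results, plasma glucose and glucose-lowering treatment, taken from routine records. A sentence in Section 10.5.2 saying whether time off drug counts towards the incidences would complete the repair.

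The cost is amendment wording and a few fields on the Follow-Up CRF.
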